Activity restrictions: Participants will be provided with an activity log-sheet to record periods of: exercise, over-night stays outside their residence (if any), time periods of open outdoor apartment windows, or other concerns. We will ask participants to sleep overnight in their bedroom at Carpenter Place during all nights of the study and to notify investigators (and note in their activity log) if they must spend a night offsite. If unexpected overnight travel occurs, this will not prohibit continued participation unless they spend a total of more than 4 days during any single study block offsite. In this case the participant will discontinue the study, and their data will be excluded from analysis due to this pre-defined protocol deviation. There are no limitations on air conditioning, heating, or indoor sources of pollution (e.g., cooking). All activities will be allowed except no exercise during periods of 24-hour BP and personal PM2.5 monitoring. We will place no restrictions on opening outside apartment windows to keep the trial as real-world as possible. In RAPIDS we did not require any restriction in this regard and nevertheless we achieved the reported significant reduction in indoor/personal PM2.5 exposures and improved BP levels. Participants will be instructed to record in their logs any periods that windows were opened to facilitate determining its impact on AFU efficacy for reducing PM2.5 exposure and BP reductions in sensitivity analyses (although there were no such adverse impacts found in RAPIDS).

Visit logistics: All study visits will commence at the same time for each participant between 8AM-10AM, after fasting for >8 hours (prior to breakfast, any caffeine) and before any medications. **All BP measurements will be obtained prior to antihypertensive medications to obtain a “trough” level, per standard clinical trial practices**⁷⁰. After visits, participants will continue daily routines (and take any medications) without restrictions.

Block 1:

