AFU intervention: We have carefully designed this study to accommodate the needs and limitations of the volunteer subjects and minimize changes and burdens on their lifestyle by incorporating noninvasive daily home BP testing while also assuring detection of outcome-exposure associations based on our previous studies. As described above in the Progress Report section, despite the fact that the RAPIDS protocol did not restrict subjects' activities (e.g., window opening), we were able to reduce personal PM2.5 exposure and observe improved CV health outcomes. Thus, we will maintain the same protocol and study real-world exposure to the extent possible. Apartment central air conditioning and heating can be used without limitations. Participants will record in activity logs any period in which windows are opened. We will employ the same commercially available AFU brand (Holmes) proven in RAPIDS to effectively reduce indoor and personal PM2.5 exposures and lower BP among participants³⁰. For the "gold standard" comparison (2-room AFU use), we will follow the same deployment protocol successfully used in RAPIDS30 and supported by EPA guidance and expert scientific opinions⁷³⁻⁷⁶. At 8AM Monday (week 1, visit day 1) of each study block, a blinded onsite investigator will place AFUs in each participant's residence. One AFU each will be placed in both the bedroom and main living room. Each AFU will be set to the randomized mode ("active" or "sham") per the description in prior sections in a *randomized double-blind fashion* by a different offsite investigator beforehand so that neither the onsite investigator nor the participant will be aware of the settings (the HEPA filter is not visible from the outside). In both rooms the AFU will be a Holmes HAP8650B-NU-1, designed for spaces up to 310 square feet. Under the "active" mode, the AFU will be fitted with a new "true HEPA" filter (Holmes HAPF600TCS), validated to remove 99.97% of particles at 0.3 μm in size⁷³. Ultrafine (10-100 nm) particles (e.g., from traffic) and larger particles (e.g., coarse PM) are typically filtered even more effectively by HEPA filters⁷³⁻⁷⁶. Under the "sham" mode, a HEPA filter will not be installed in the AFU and there will be no significant removal of PM2.5. Each AFU will be fitted with a cumulative power consumption meter (Kill-A-Watt EZ) to verify continuous operation at the correct fan speed setting for the entire intervention period. The low noise level of the AFUs will be indistinguishable between active and sham

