7. Disseminate findings for broader application by health professionals through channels of peer-reviewed publications and presentations at conferences on aging.

Statistical Analyses and Data Management

Sample size, power considerations, and statistical analysis plans are provided in full in the Study Record: the PHS Human Subjects and Clinical Trials Information document.

Project Management and Schedule

As described in the multiple PI leadership plan, Drs. [name] and [name] together will provide oversight of the entire project. Since the proposed research is interdisciplinary and involves multiple schools/departments, a governance structure will be implemented in order to ensure effective management and coordination. The proposed research will follow a work plan that will meet the milestones shown in the “Study Timeline” attached to the Study Record: the PHS Human Subjects and Clinical Trials Information document. We will hold bi-monthly general project meetings involving all staff and investigators to present the latest data and to coordinate study logistics and analysis. The team of investigators on this proposal is well-poised to integrate their various disciplines and ensure a high probability of success for accomplishing the proposed specific aims.

DATA MANAGEMENT AND STATISTICAL CONSIDERATIONS

Study Power and Analysis Plans:

With 50 subjects randomized to blocks 2 (“bedroom alone AFU”), and (“control”) in a random sequence, we anticipate adequate power using our proposed cross-over study design for observing significant reductions in **average systolic BP (primary endpoint)**. With the repeated BP measurements collected in this cross-over design, we will do paired analysis for power calculations, since each subject can serve as their own control given sufficient washout periods and because we have a priori pre-specified the group comparison hypothesis for each aim clearly beforehand. We will be able to achieve 90.3% power in **Aim 1a** for detecting a 3 mm Hg in mean systolic BP difference comparing the “bedroom AFU” to the “control” group at both the acute (4-day) and chronic (4-week) time periods, assuming that the standard deviation (SD) of systolic BP is 8.2 mm Hg. The detectable mean difference of systolic BP between “bedroom FU” vs “control” with the corresponding statistical powers that we can achieve is as follows:

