Both the primary endpoints and the secondary measures such as diastolic BP, 24-hour BP levels and HOMA-IR will be reported as mean (median) \pm SD (IQR). One-sample paired t-test will be performed to compare each outcome variable between active intervention group and the control group. In case there are extreme values or that the variables are not normally distributed, Wilcoxon signed-rank test, a non-parametric test for comparing repeated measurements' mean ranks, will be performed for robustness¹. When the distribution of an outcome variable is not anticipated to follow a normal distribution, we will transform it to meet normality assumptions as best as possible before we fit regression models to adjust for confounders (age, sex, BMI, dose of BP tablets, type of BP control medication). Non-parametric correlation coefficients, such as Kendall's tau⁷ or spearman's rho⁸, between the principal outcomes and exposure measures will be calculated at each time point. Such measures provide robust inferences. Multiple hypothesis testing will be adjusted through the Holm's procedure⁹.

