More specifically, to adjust for other confounders, we will use linear mixed models²⁻⁴ to evaluate the effect of interventions on the outcomes (e.g. BP levels) adjusting for confounders. The mixed models will fully represent the structure of the data by taking into account the within-subject correlations of the outcome variables measured repeatedly at different time points over the study design. We will also evaluate the impact of other variables that may impact the results. To be more specific, a mixed effect model with a random intercept and a random slope²⁻⁴ will be fit for the longitudinal measurement of the outcomes: $Y_{ij} = a_0 + a_1 t_{ij} + a_2 I(B_{ij} = 1) + a_3 I(B_{ij} = 2) + a_4 X_{ij} + b_{i0} + b_{i1} t_{ij} + e_{ij}$, where Y_{ij} denotes the repeated average BP outcomes for subject i at occasion j , B_{ij} denotes what intervention is subject i randomized to at occasion j , and X_{ij} are the other covariates that would be controlled in the model (age, sex, BMI, dose of BP tablets, type of BP control medication). So in **Aim 1a**, we hypothesize $a_2 \neq 0$ and test for $H_0 : a_2 = 0$, and in **Aim 2a**, we hypothesize $a_3 \neq 0$ and test for $H_0 : a_3 = 0$, and in **Aim 2b**, we are testing $a_2 = a_3$. Similar models will be fit for other secondary outcome variables, such as ABPM, HOMA-IR, etc. When it happens some outcome variables have inflated zero measures, we will adopt zero-inflated regression models or a two-part mixture regression (tobit) model^{5,6} on the outcome changes between “active intervention” vs. “control”.

Other statistical considerations:

Missing data: We will try to avoid missing data when collecting data through the study design. When missing data happens, we will test if the data are missing completely at random (MCAR). If it is MCAR or the amount of missing data is less than 10%, analysis will be performed based on the complete data. If the amount of missing data is more than 10%, multiple imputations (5-10 times) will be utilized through mi package in R¹⁰. The analysis will be performed on each imputed data set, and later merged through mitools package in R¹¹. Multiple imputations are based upon the missing-at-random (MAR) assumption¹². Sensitivity analysis¹³ will be examined when inferences depart from the MAR assumption.

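### The only written PM2.5–BP analysis correlates levels across different people at each time point, so it mixes randomised exposure differences with lasting differences between people

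*Combined protocol and SAP*

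**What the plan says.** Under Study Power and Analysis Plans, rank correlations "between the principal outcomes and exposure measures will be calculated at each time point", and the plan credits them with robust inference. The next sentence reads "Multiple hypothesis testing will be adjusted through the Holm's procedure", without saying which tests form the family. Nothing there describes the correlations as within-person, change-score, partial or repeated-measures.

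The treatment comparisons are handled differently. The power argument is that "each subject can serve as their own control given sufficient washout periods", and "One-sample paired t-test will be performed to compare each outcome variable between active intervention group and the control group". The linear mixed model has a random intercept and slope. Its fixed terms are time, intervention indicators and covariates, which "are the other covariates that would be controlled in the model (age, sex, BMI, dose of BP tablets, type of BP control medication"). PM2.5 is not a term.

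Under Protocol Modifications, blood draws are removed. Personal PM2.5 is measured once per block at the end of week 4, bedroom PM2.5 is recorded throughout both blocks, and home BP is taken in weeks 1 and 4 of each block.

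**The concern.** Linking exposure to outcome is a stated purpose: the AFU intervention section speaks of "assuring detection of outcome-exposure associations based on our previous studies". The one analysis written for it ignores what the crossover offers, which is an active and a sham value of both PM2.5 and BP for every participant.

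Lasting differences between people are to be expected. Under Activity restrictions, "There are no limitations on air conditioning, heating, or indoor sources of pollution (e.g., cooking"), and windows may be opened freely. Eligible systolic BP runs from 115 to 160 mm Hg, against a sought effect of 3 mm Hg. If people with dirtier indoor air also tend to have higher BP for other reasons, the coefficient can be clearly positive with no PM2.5 effect behind it. If the tendency runs the other way, it can hide one. The plan names age, sex, BMI and BP medication as confounders for its regressions but leaves the correlations unadjusted. At stake is any statement that BP fell because PM2.5 fell.

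**Working it through.** **No plan figure to reproduce.** The plan gives no power, alpha or sample size for these correlations. Two-sided 0.05 is assumed.

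**What is written about PM2.5 and BP together**
- Paired t-test or signed-rank test: effect of assigned mode on each outcome.
- Mixed model: effect of assigned mode, with no PM2.5 term.
- Mediation (Aim 3b): no model given, and the blood samples it needs were removed.
- Rank correlations at each time point: the only one that relates PM2.5 to BP.

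**Inputs for an illustration**
- From the documents: n = 50; sham personal PM2.5 of 15.7 µg/m³ (prior trial); systolic SD 8.2 mm Hg.
- Assumed: SD of usual PM2.5 6 µg/m³; mean reduction 45% with SD 15 points; half the participants on active.
- BP, low case: between-person SD 6.8 and within-person SD 4.6, since √(6.8² + 4.6²) = 8.2. The implied within-person correlation, 46.2/67.4 = 0.69, is close to the 0.70 at which the plan's 90.3% power is recovered (90.6%).
- BP, high case: between-person SD 14 and within-person SD 4.5. A uniform spread over 115–160 would have SD 45/√12 = 13.0, so 14 is near the top of what eligibility allows.
- Confounding c: mm Hg higher BP per SD of usual PM2.5, set at 0, 2 or 4. No source in the documents.

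**Spread of PM2.5 at one time point**
- Active mean: 0.55 × 15.7 = 8.64.
- Active variance: 0.55² × 36 + 0.15² × (15.7² + 36) = 10.89 + 6.36 = 17.25.
- Mixed variance: (36 + 17.25)/2 + ((15.7 − 8.64)/2)² = 26.6 + 12.5 = 39.1, SD 6.25.
- The randomised active–sham shift supplies 12.5/39.1 = 32% of it.

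**Expected correlation with no true PM2.5 effect**
- Covariance: c × (6 + 0.55 × 6)/2 = 4.65c.
- r = 4.65c / (6.25 × SD of BP), where SD of BP is √(14² + 4.5²) = 14.7 (high) or 8.2 (low).
- Rejection rate ≈ Φ(√47 × atanh r − 1.96). With n = 50, |r| of about 0.28 reaches p < 0.05.

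| c (mm Hg per SD) | Between-person BP SD | r | Approximate rejection rate |
|---|---|---|---|
| 2 | 14 | 0.10 | 10% |
| 2 | 6.8 | 0.18 | 24% |
| 4 | 14 | 0.20 | 29% |
| 4 | 6.8 | 0.36 | 74% |

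This is a Pearson approximation, in which the between-person SD includes the confounded part. Simulation of the rank test gives somewhat lower rates: about 5% at c = 0, 9–21% at c = 2 and 20–70% at c = 4.

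**A separately parameterised simulation.** Here usual PM2.5 has SD 4, within-person PM2.5 SD 3, and BP SDs are 6.8 and 4.6. False positives are 4% at a person-level PM2.5–BP correlation of 0, about 20% at 0.3 and 43% at 0.5. For comparison, c = 4 with SD 6.8 is a person-level correlation of 4/6.8 = 0.59, and c = 2 with SD 14 is 2/14 = 0.14.

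**Within-person analysis.** The BP difference between blocks contains no fixed person term, so c drops out. Simulated false positives are about 5% throughout (4–6%).

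**The case against.** The strongest reply is that this is a supplementary calculation. No aim and no row of Table 1 rests on a PM2.5–BP correlation, the text says the coefficients are calculated, and secondary comparisons are called hypothesis-generating. That stands as a limit on importance. It does not settle the matter, because the same passage claims robust inference and moves straight to a multiplicity adjustment.

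Three stronger readings are tempting, and the documents do not support them.
- A reader might infer that the crossover is discarded altogether. It is not: BP is compared within person, and the plan applies the same methods to PM2.5. Only the link between the two changes is missing.
- A reader might treat all the PM2.5 spread as confounded. With about half the participants on active, part of it is randomised. A false-positive rate near 41% at between-person SD 14 and c = 4 needs everyone on sham at that time point; with half on active it is 20–25%. The plan does not define a time point, so this should be stated.
- A reader might infer that the correlation will probably miss a real effect. That depends on the assumed SDs. With between-person SD 6.8 and a true slope of 3/6.6 = 0.455 mm Hg per µg/m³, the per-time-point test can have more power than a correlation of within-person differences (60% against 39%).

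Finally, the protocol refers to a separate Study Record for its full statistical plan. That record was not available, so a within-person exposure model there cannot be excluded.

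**Conclusion.** The point holds for the exposure–response analysis only. As written, that analysis compares different people, and its validity depends on usual PM2.5 being unrelated to other causes of BP, which the design does nothing to ensure. The active-versus-sham conclusion on BP does not depend on it.

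The direction of the problem is firm; its size is not. The false-positive range, from about 5% up to 70%, rests on assumed variance components and an assumed strength of confounding, and its top end needs a strong person-level association. No general power ranking against a correlation of differences is claimed. This is a minor but worthwhile correction.

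**What to change.** Name the mixed model as the exposure–response analysis. Enter PM2.5 as person mean and within-person deviation, add a period term, and report the within-person slope with its interval, using week-4 active and sham PM2.5 and home systolic BP. In this model PM2.5 should take the place of the intervention indicators; otherwise the slope loses the randomised mean shift. A plain correlation of differences also loses that shift, which is why the slope is preferred. In the simulated scenarios, with a true slope of about 0.46, the slope kept 96–99% power and about 5% false positives. With two week-4 values per person, a random intercept is enough.

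Define time point, keep the per-time-point correlations as descriptive, and drop the claim of robust inference for them.

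The cost is SAP wording and a little analysis work. The within-person slope is still partly non-randomised, since window opening and fan setting can differ between blocks, so it should be called supportive.

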Aim 1: Determine if long-term AFU usage provides sustained reductions in PM2.5 exposure and persistent improvements in cardiometabolic outcomes. We propose a randomized double-blind 2-way crossover study (AFUs bedroom- vs. sham filtration) in 50 adults living in a low-income senior residence impacted by roadway pollutants. We posit that compared to sham, AFU use *long-term* (4-week) periods will **(1a)** lower resting morning BP (*primary outcome*), **(1b)** reduce indoor PM2.5 and 24-hr personal PM2.5 exposures, and **(1c)** improve secondary health outcomes: 24-hr and nocturnal BP, 24-hr and nocturnal aortic hemodynamics (BP, augmentation index), and insulin sensitivity.

Aim 2: Determine if nocturnal PM2.5 exposure reduction alone improves cardiometabolic outcomes. We posit that compared to sham, bedroom-only AFU use will **(2a)** lower resting morning BP. We further posit that **(2c)** 24-hr personal PM2.5 exposure and **(2d)** secondary health outcomes will improve – particularly nocturnal BP (a powerful

predictor of CV events)³³⁻³⁵.

Aim 3: Demonstrate the key role of adrenal activation as a novel mechanism explaining PM2.5-induced cardiometabolic effects. Recent data suggest PM2.5 provokes hypothalamic-pituitary-adrenal axis (HPAA) activation³². We posit **(3a)** AFU will reduce adrenal activation (comprehensive assessment by blood steroidomic profiling) after 4 weeks. Steroids with glucocorticoid and mineralocorticoid activity will be shown **(3b)** to be mediators of PM2.5-induced BP changes & insulin resistance.

PM2.5 is a leading risk factor for mortality. Our proposal, which will help validate the benefits of novel strategies to employ AFUs in an elderly vulnerable population living in a non-traditional setting, is directly responsive to the Program Announcement (PA-18-142), and is of global public health importance. Positive results would form a key part of the evidence base required to promote more wide-scale AFU use. In the long term, given the low cost and burden, AFU use could be up-scaled to help protect diverse populations across the world.

RESEARCH STRATEGY

SIGNIFICANCE

PM2.5 is a major contributor to the global epidemic of cardiometabolic diseases.

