Enrollment: Interested residents will call the study research coordinator. Study inclusion/exclusion criteria will be reviewed (no changes). All subjects must attest to be non-smokers living in non-smoking household. Consents will be left at the office or subjects will be emailed or mailed the consent form and subjects will be given ample time to review the consent and consider their participation independently. Study team will review the consent document over the telephone just as they would during a face to face meeting. Signature will be obtained on the consent form and provided to the study staff via mail or left for pickup by study staff in the same manner as equipment is dropped off with no contact. This cohort is unlikely to benefit from electronic consenting procedures based on the lack of internet access, the poor internet provided by Carpenter Place, the willingness of the participants, and the added burden it would place on this older population of subjects participating in a low risk study.

Study Flow: The modified trial will be conducted per the original design except for no face-to-face interactions between research staff and subjects and the protocol has been simplified. Subjects will be assigned a research ID number. They will be randomized in a blinded fashion to either active vs sham PAC use for intervention block 1. After completing block 1, they will washout for 1 week and then crossover to block 2 and undergo the same trial randomized to the alternative PAC intervention (sham vs active).

BLOCK 1 (2)													Washout	
	Week 1 (6)					Wk 2-3 (7-8)		Week 4 (9)						
	Day					Day								
	1 M	2 T	3 W	4 Th	5 F			1 M	2 T	3 W	4 Th	5 F		
PAC INTERVENTION (2 limb x-over)														
Randomized PAC	↓	x	x	x	x	----->	x	x	x	x	x	↑		
TESTING														
Home BP: AM		✓	✓	✓	✓			✓	✓	✓	✓	✓		
PM		✓	✓	✓	✓			✓	✓	✓	✓	✓		
PM MONITORING														
In-room PM (Purple Air)	↓	x	x	x	x	----->	x	x	x	x	x	↑		
Personal PM (PDR1500)											↓	↑		

↓ = start; x = continue; ↑ = stop; ✓ = check BP; -----> = continues throughout period

Week-1/day-1: PAC Intervention/bedroom PM monitoring: Start in subject's bedroom at 9 am

Home BP: am= when first wake up in bedroom; pm=just before going to sleep in bedroom

Personal PM monitoring: Wear/have on person during daytime. Put by bedside at night-time.

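### The adjusted mixed model does not fit the two-block crossover: with one BP value per block its random slope cannot be identified, and with both BP weeks it lacks a subject-by-block term

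*Combined protocol and SAP*

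**What the plan says.** The Specific Aims describe a two-condition crossover: "We propose a randomized double-blind 2-way crossover study (AFUs bedroom- vs. sham filtration". The Study Flow in the Protocol Modifications section says "They will be randomized in a blinded fashion to either active vs sham PAC use for intervention block 1", with the alternative mode in block 2. The mode stays fixed for the whole block (Block 1, week 1/day 1). The modified schedule has home BP on Tuesday to Friday of weeks 1 and 4 of each block. That is four BP weeks per person, at calendar weeks 1, 4, 6 and 9.

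Study Power and Analysis Plans then gives two analyses. The first is simple: "One-sample paired t-test will be performed to compare each outcome variable between active intervention group and the control group". The second is a linear mixed model, introduced to adjust for confounders, of which the plan says "The mixed models will fully represent the structure of the data by taking into account the within-subject correlations of the outcome variables", these being "measured repeatedly at different time points over the study design". Its random part is "b_{i0} + b_{i1} t_{ij} + e_{ij", and its response "denotes the repeated average BP outcomes for subject i at occasion j". The equation carries two intervention indicators. Aim 1a is tested by a_2, Aim 2a by a_3, and Aim 2b by their equality.

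The plan does not define occasion or t. It gives no residual covariance structure or degrees-of-freedom method, and does not say whether the paired test or the mixed model decides Aim 1a.

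**The concern.** Each person is assigned a filter mode only twice, once per block. Anything that moves a person's BP for a whole block and then resets is shared by both BP weeks of that block, so it does not average out within the block. A model whose error structure has no block level counts the two weeks as separate evidence on active versus sham.

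The adjustment covariates do not repair this. Age, sex and BMI are essentially constant within a person, and medication is meant to be stable during the study.

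At stake are the standard error and interval for the Aim 1a coefficient; the estimate itself is essentially unbiased. With two analyses and no stated precedence, the mixed model could report BP lowering where the paired test does not.

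**Working it through.** **1. The plan's own figure.** The plan gives no standard error or error rate for the mixed model. Its only related figure is 90.3% power for 3 mm Hg with n=50 and SD 8.2. A two-sided paired t-test at 5% (alpha assumed) with 8.2 as the SD of the difference gives 71.8%. Reaching 90.3% needs an SD of the difference of 6.38, that is, a correlation of 1 − 6.38²/(2 × 8.2²) = 1 − 40.7/134.5 = 0.70, which is not stated. So the plan supplies no within-person variance, and the scale used below is an assumption.

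**2. One value per block.** Two values per person give 2 variances + 1 covariance = 3 quantities. The model needs an intercept variance, a slope variance, their covariance and a residual variance = 4. With the common 1-week washout, t takes the same two values for everyone, so no further information arises. Fixing the covariance at zero would leave 3 for 3, but the plan states no such restriction. Three blocks would have given 3 + 3 = 6 quantities, which is enough.

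**3. Both weeks, closed form (slope variance zero).** Let τ² be the person-by-block variance, σ² the weekly residual variance, W = τ² + σ², and s = τ²/W.
- True variance of a person's difference in block means: 2τ² + σ² = W(1 + s).
- The model pools one between-block contrast (mean square σ² + 2τ²) with two within-block contrasts (σ² each): σ² + 2τ²/3 = W(1 − s/3).
- True SE / model SE = √[(1 + s)/(1 − s/3)]: √(1.10/0.967) = 1.067 at s = 10%, √(1.25/0.917) = 1.168 at 25%, and √(1.50/0.833) = 1.342 at 50%.
- A nominal 5% test then rejects in 6.6, 9.3 and 14.4% of null trials.

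**4. Both weeks with the random slope (REML simulation).** Inputs: 25 people per sequence, weekly averages at weeks 1, 4, 6 and 9, SD 8.2, assumed within-person correlation 0.5 (between- and within-person variance 33.6 each), 4,000 null trials per cell (Monte Carlo SE about 0.35 point at 5%). The share s is assumed.

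| s | Block SD, mm Hg | Planned model: mean SE v true spread | Type I %, z (t48) | With subject-by-block and period, t48 % | Paired t on block means % | Significant by mixed model only / paired only % |
|---|---|---|---|---|---|---|
| 0 | 0 | 0.827 v 0.815 | 4.7 (4.1) | 3.7 | 4.5 | 1.1 / 0.9 |
| 10% | 1.8 | 0.822 v 0.880 | 6.6 (6.1) | 4.9 | 4.8 | 2.3 / 0.5 |
| 25% | 2.9 | 0.817 v 0.923 | 8.9 (8.1) | 5.1 | 4.7 | 4.3 / 0.1 |
| 50% | 4.1 | 0.800 v 1.026 | 13.4 (12.3) | 5.6 | 5.3 | 8.1 / 0.0 |

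Smaller repeat simulations (800 to 1,500 trials per cell) gave 5.0 to 6.8% at s = 0, 7.3 to 8.5% at 25% and 11.9 to 13.2% at 50%. The slope on calendar time therefore absorbs only part of the missing term. If t is coded as week within block it absorbs nothing, and step 3 applies. Type I error depends on s, not on the SD. Over the plan's SD range of 6.2 to 9.8 and correlations of 0.5 to 0.7, the block SDs for the three non-zero shares become 1.1–2.2, 1.7–3.5 and 2.4–4.9 mm Hg.

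**5. Other patterns.** Under smooth calendar decay (time constants 2, 4 and 8 weeks; shares 25 and 50%; 2,000 trials per cell) the planned model stays at 4.6 to 6.5%. Weeks 4 and 6, across the washout, are closer in time than weeks 1 and 4 within a block, so only a component that resets between blocks does harm. If occasions are days, with no subject-by-week variance, type I error is 4.6, 7.0, 9.0 and 15.9% at s = 0, 10, 25 and 50%.

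**The case against.** The strongest reply is that the plan never commits to pooling both weeks. A reader might infer pooling from the random slope, since two values per person cannot support one. That inference is not safe, because the slope may be a remnant of a three-block design. The equation has two active indicators. The blood-draw section refers to Blocks 1-3, the power text to a block 3, and the exclusion criteria to 14 weeks (3 × 4 weeks plus two washout weeks). With three blocks, one value per block would identify the slope.

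Other text also fits one value per block. The power statement treats the acute and 4-week comparisons as separate. The outcome is a 4-day average within one week. Similar models are planned for HOMA-IR, for which blood was to be drawn once per block before blood draws were removed. Finally, an unaffected paired test is already specified, and power is based on it.

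All of this stands, and it leaves both readings open. It does not rescue the equation, which in the current two-block design cannot be fitted as written to one value per block. Nor does the paired test settle the matter while Aim 1a is also attached to a_2 and no precedence is stated.

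**Conclusion.** The mixed model needs rewriting on either reading: its random slope is unidentifiable with one value per block, and its error structure is incomplete with two.

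A reader might conclude that the trial's type I error is 8 to 13%. The documents do not support that. Those figures require both weeks in one model, independent residuals, and a component that resets between blocks and makes up 25 to 50% of within-person variance. No document shows or sizes one. A possible source is the home BP monitor, which is returned after each block and reissued, with no statement on whether the same unit comes back. The larger RAPIDS reduction in obese participants (6.9 against 3.2 mm Hg overall) hints at person-specific response, but it is post hoc and comes from a two-room intervention.

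At a share of 10% or less, type I error is at most about 6 to 7% in the main simulation. The paired test is sound throughout. This is a worthwhile correction to the adjusted analysis, held with moderate confidence; it is not a defect in the trial design.

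**What to change.** Define occasion and t, and write the equation for two conditions with a single treatment coefficient. Then choose one route:

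1. If both weeks enter one model, add a random subject-by-block intercept and a fixed period term, with Satterthwaite or Kenward-Roger degrees of freedom. Keep the random slope only if it can be estimated. Add a subject-by-week term if daily values are used.
2. Either analyse week 1 and week 4 separately, with one value per block and no random slope, or state that the paired analysis on one block-level value per person is primary for Aim 1a and the mixed model supportive.

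The cost is SAP text only, with no new data; naming the paired analysis as primary takes one sentence. For route 1, if there is no block variance, the mean SE rises from 0.827 to 0.843 (about 2%). Power for 3 mm Hg then falls from 94.2% to 93.7% under the assumed variances. At shares of 10, 25 and 50% the SE rises 5, 11 and 24% (to 0.859, 0.905 and 0.990), close to the true spread.
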